Therapies for Recovery of Hand Function After Stroke

NCT03574623

Study Protocol and Statistical Analysis Plan

Note: The text below was extracted from the IRB protocol for this study, which was first approved on January 22, 2018. The most recent amendment to the protocol was approved on:

April 19, 2023

Study Protocol

Abstract

This is the first multi-site clinical trial of contralaterally controlled functional electrical stimulation (CCFES). CCFES is an innovative technology and rehabilitation therapy for improving the recovery of hand function in patients with upper extremity hemiparesis. CCFES applies electrical stimulation to the paretic finger and thumb extensor muscles through surface electrodes, causing the weak hand to open, a function that is often lost in stroke survivors. The patient controls the intensity of stimulation to their paretic hand by wearing a glove with sensors on their unaffected contralateral hand. When the patient opens their unaffected hand, a proportional intensity of stimulation opens their paretic hand. CCFES puts the patient back in control of their paretic hand, and this may drive neuroplastic changes that lead to better recovery of hand function. The central hypothesis is that CCFES is more effective for recovery of hand function than conventional cyclic neuromuscular electrical stimulation (cNMES) therapy or task oriented training (TOT) without electrical stimulation. Stroke survivors between 6 and 24 months post-stroke will be randomized to 12 weeks of CCFES, cNMES (which applies electrical stimulation to the hand extensors but with pre-set timing and intensity), or TOT without electrical stimulation. This study will determine if CCFES can be administered with positive results at other sites, will establish the clinical efficacy of CCFES (comparison with cNMES), and will generate initial estimates of effectiveness of CCFES (comparison with TOT).

Specific Aims

AIM 1. Compare the effects of CCFES and cNMES in improving hand function after stroke.

Research Hypothesis: At 6 mo post-treatment, improvements in hand function will be significantly greater after CCFES than cNMES, and a greater proportion of participants will achieve clinically significant improvements after CCFES than cNMES. Outcomes will include measures of dexterity, upper extremity activity limitation and impairment, and patient-reported outcomes.

AIM 2. Compare the effects of CCFES and TOT in improving hand function after stroke.

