Research Hypothesis: At 6 mo post-treatment, improvements in hand function will be significantly greater after CCFES than TOT, and a greater proportion of participants will achieve clinically significant improvements after CCFES than TOT.

Methods and Procedures

This is a 4-site, assessor-blinded Phase II randomized controlled trial to determine whether CCFES is superior to cNMES or TOT in improving hand function in patients with upper extremity hemiplegia who are between 6 and 24 months past their stroke. A target of 132 patients will be randomized to Contralaterally Controlled Functional Electrical Stimulation (CCFES), Cyclic Neuromuscular Electrical Stimulation (cNMES), or Task Oriented Training (TOT). Stratification factors include age, severity of hand impairment, months post-stroke, and treatment site.

All groups will receive 12 weeks of upper limb rehabilitation treatment consisting of a home regimen and functional task practice in the lab. Treatment will include: 1) therapist-administered 90-min sessions of hand task practice twice a week in the lab, and 2) self-administered sessions lasting approximately 1 hour per session 10 times a week at home.

- CCFES group: 90-min 2x/week CCFES therapy with therapist + 10x/week CCFES hand opening exercise self-administered at home.
- cNMES group: 90-min 2x/week therapy with therapist + 10x/week cNMES hand opening exercise self-administered at home.
- TOT group: 90-min 2x/week therapy with therapist + 10x/week home exercise program self-administered at home.

All subjects will be followed for 6 months post-treatment. Blinded assessments will take place at baseline, mid-treatment (6 wk), end-of-treatment (12 wk), and at 3- and 6-months post-treatment.

Baseline characteristics will be collected, including demographic (e.g., sex, age, race, pre-morbid hand dominance), stroke-related (e.g., time post-stroke, hemorrhagic or ischemic, cortical or subcortical, right or left, Stroke Impact Scale score), and neurologic data (e.g., side of hemiparesis, cognition,

depression, neglect, visual deficits, aphasia), as well as co-morbidities, and medications. The balance of these between the three groups and their effect on the outcomes will be evaluated.

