The primary analysis was based on a modified intention-to-treat (ITT) sample, which included participants in the group to which they were assigned who completed the treatment phase of the study. For all measures, changes from baseline were modeled using a linear mixed effects modeling approach, which accounts for missing values using maximum likelihood estimation. The linear mixed effects model using the restricted maximum likelihood (REML) estimator was employed, along with the Satterthwaite approximation to estimate the denominator degrees of freedom. While REML assumes normality of the random effects and residuals, it is generally more robust to violations of this assumption than traditional maximum likelihood, particularly in the estimation of fixed effects. The model included a random intercept to account for individual variability, and we specified a compound symmetry covariance structure to model the within-subject correlations. Least squares mean estimates were calculated after fitting each model for each group at each timepoint and were used to quantify within-group changes from baseline and between-group differences in change from baseline to 6 mos post-treatment. Statistical significance was set at $p < 0.05$. No adjustments were made for multiple comparisons in order to maintain a balance between Type I and Type II error rates. This balanced approach to error control was prioritized rather than strictly minimizing Type I error at the expense of statistical power and increasing the risk of overlooking meaningful effects. Pair-wise Chi-square tests were used to compare responder rates between groups.

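### The SAP gives no handling for a missing 6-month responder status, so by default the chi-square tests drop people lost after week 12 whose earlier scores the mixed model uses

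*Combined protocol and SAP*

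**What the plan says.** Under Specific Aims, each research hypothesis has two parts, both placed at 6 months post-treatment. For Aim 1 the first part is "At 6 mo post-treatment, improvements in hand function will be significantly greater after CCFES than cNMES" and the second is "a greater proportion of participants will achieve clinically significant improvements after CCFES than cNMES". Aim 2 has the same structure, ending in "a greater proportion of participants will achieve clinically significant improvements after CCFES than TOT".

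The Statistical Analysis Plan treats the two parts differently. For mean change, "changes from baseline were modeled using a linear mixed effects modeling approach, which accounts for missing values using maximum likelihood estimation". For responders, the whole provision is "Pair-wise Chi-square tests were used to compare responder rates between groups". That sentence names no outcome measure, threshold or time point, and gives no rule for a participant with no 6-month score.

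The primary sample is a modified ITT set of participants "who completed the treatment phase of the study". Attending the 6-month visit is not a condition. The assessment schedule (Methods and Procedures) reads: "Blinded assessments will take place at baseline, mid-treatment (6 wk), end-of-treatment (12 wk), and at 3- and 6-months post-treatment".

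**The concern.** A participant who finishes treatment and is then lost belongs to the primary set and will normally have baseline, 6-week and 12-week scores, perhaps also a 3-month score. The mixed model uses these. A chi-square test needs a yes or no for each person and makes no use of earlier visits. Unless a status is assigned by some rule, that person drops out of the responder comparison.

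The two parts of one hypothesis could then rest on different people and different assumptions. The mixed model needs missingness to depend only on observed data. An observed-case estimate of a responder rate needs missingness to be unrelated to response within the arm, which is stronger. The trial is described as assessor-blinded, and participants can see whether they have a glove, a stimulator or neither. Follow-up runs 6 months after treatment ends. Loss related to perceived benefit, and unequal across arms, is therefore plausible, though nothing in the documents shows it. With no stated rule, the choice of handling also stays open after the data are seen.

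**Working it through.** **Is a rule stated anywhere?** The likelihood-based handling is attached to the modelled changes from baseline, not to the chi-square tests. The two sensitivity analyses (all randomized; at least 80% of treatment with no other upper limb therapy) change who is included. Neither says how a missing responder status is classified.

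**Inputs.** From the documents: 132 randomized in three groups. Assumed: equal allocation, 132 / 3 = 44 per arm, all completing treatment; change SD 8; correlation 0.7 between visits; responder threshold 6; mean change 6 in both arms (no true difference). The plan gives no responder figure to reproduce.

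**Bias, closed form.** One arm loses 10% at random. The other loses 5% of those above and a fraction L of those below the week-12 mean. With bivariate normal scores and a threshold equal to the mean, the full-data responder rate is 0.5, and

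- P(responder | above mean at week 12) = 1/2 + arcsin(0.7)/π = 0.747
- P(responder | below) = 1 − 0.747 = 0.253
- observed rate = [0.95 × 0.747 + (1 − L) × 0.253] / (1.95 − L)

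| L | Loss in that arm | Observed rate | Bias in that arm |
|---|---|---|---|
| 15% | 10% | 0.514 | +1.4 points |
| 25% | 15% | 0.529 | +2.9 points |
| 35% | 20% | 0.546 | +4.6 points |

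The arm with random loss is unbiased, so the difference moves against it by these amounts. Simulation gives the same: 1.4, 2.9 and 4.7 points. The standard error of the difference is about 11 points, so the bias is roughly 0.1 to 0.4 standard errors. The simulated false-positive rate was 5.7%, 5.9% and 6.7%.

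**When loss does not differ by arm.** If both arms lose people by the same rule and there is no true difference, the biases cancel (about 0). In a separate simulation with a true difference of about 14.7 points (mean changes 6 and 3) and low scorers leaving both arms, observed-case data gave 15.6 points, about 1 point off. Random loss gave 14.7, no bias.

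**A harsher case.** In that second simulation, with about 17% lost per arm and strong dependence on the earlier score, high scorers leaving CCFES and low scorers the comparator gave 4.5 points; the reverse gave 26.0. Imputing from the earlier score gave 14.6 to 14.9. This opposite-direction pattern is an outer bound, not an expectation.

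**Precision.** Losing 10% in both arms inflates the standard error by √(1/0.90) = 1.05; losing 20% in both, by √(1/0.80) = 1.12. Across the simulated patterns the inflation was 5% to 14%. Multiple imputation within arm from earlier visits brought it to within 3% of full data, with bias at or below 0.3 points.

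**Does the unstated rule matter on one data set?** Take 7 of 44 missing per arm, with 18/37 and 11/37 observed responders (Pearson chi-square, no continuity correction):

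- observed cases: 18/37 − 11/37 = 18.9 points, p = 0.096
- missing = non-responder: 18/44 − 11/44 = 15.9 points, p = 0.112
- extreme bounds: 18/44 − 18/44 = 0.0 points (p = 1.0) to 25/44 − 11/44 = 31.8 points (p = 0.002)

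**The case against.** A reader might infer that the responder test can use only people seen at 6 months, or that the plan chose to drop the others. The documents do not say so. Missing = non-responder, carry-forward or imputation would each fit the one sentence given. Dropping people is the natural default of a silent plan, not a stated rule. The 6-month time point also comes from the aims and not from the SAP sentence, and nothing ties responders to the BBT.

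A reader might also infer that the responder comparison is necessarily biased. It is not: random loss produces no bias, and loss by the same rule in both arms produces almost none in the difference. Material bias needs loss that is related to outcome and differs by arm. The documents give no dropout rate from which to judge how likely that is.

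Finally, the primary endpoint is BBT change at 6 months, and the responder comparison is not given primary status. Calling it half of each hypothesis describes the sentence and not its weight in the plan.

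These points stand and limit the concern. They do not remove it: a comparison named in both aims has no stated missing-data handling, and its default discards scores already collected on members of the primary set.

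**Conclusion.** The concern holds as an omission whose default is inferior to an available method. The responder comparison lacks a definition, a restated time point and a rule for missing 6-month status, and the mixed model's handling of missing values does not carry over to it. Under the assumed inputs, the default costs 5% to 14% in standard error. It adds bias of roughly 1.5 to 4.5 points when loss is selective in one arm and random in the other, and more only under the extreme opposite-direction pattern. All these sizes depend on assumed loss rates, SD, correlation and threshold. The mean BBT analysis and the primary endpoint are untouched. The change should be made, but it does not threaten the main result.

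**What to change.** 1. State for each responder analysis the outcome measure, the threshold for clinically significant improvement, and that status is assessed at 6 months post-treatment.
2. For each such measure, multiply impute the missing 6-month change within arm from the baseline, 6-week, 12-week and 3-month scores. Classify each imputed value against the threshold, and combine the pair-wise differences in proportions with Rubin's rules.
3. Report the observed-case chi-square test and missing = non-responder as sensitivity analyses, with the number missing at 6 months in each arm.

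Cost: a few sentences in the SAP and a short program on data already collected. Because the SAP is written in the past tense, this would probably be a supplementary analysis, labelled as such. The small downside is reliance on an imputation model; its missing-at-random assumption is the one the mixed model already makes.

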Exploratory subgroup analyses were performed using mixed effects models to test whether covariates (e.g., site, months since stroke, dose received, sex) moderated the change in BBT, UEFM, and ARAT scores across groups. A pre-planned analysis of only those participants with moderate hand weakness at baseline was conducted based on the prior study showing participants with moderate weakness achieved greater gains on the BBT than participants with severe hand weakness. Two pre-planned sensitivity analyses of the motor recovery outcomes were done. The first included all participants who were randomized to a treatment group regardless of the amount of treatment received. The second included only participants who received no other upper limb physical therapies during the treatment period and completed at least 80% of the planned treatment, i.e., at least 18 out of 22 FTP visits and at least 8 out of 10 home exercise sessions per week on average.

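### Responder rates are compared by an unadjusted chi-square test although randomisation is stratified by hand-impairment severity, so power is lost if severity predicts response

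*Combined protocol and SAP*

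**What the plan says.** Methods and Procedures describes a four-site, three-arm trial with a target of 132 participants. On allocation it says "Stratification factors include age, severity of hand impairment, months post-stroke, and treatment site". Neither the cut-points nor the randomisation method is given.

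Specific Aims, Aim 1, hypothesises that "a greater proportion of participants will achieve clinically significant improvements after CCFES than cNMES", after a first part about mean improvement. Aim 2 repeats both parts for CCFES against TOT.

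For the responder part, the SAP's whole analysis is "Pair-wise Chi-square tests were used to compare responder rates between groups". No stratified or covariate-adjusted version appears. The responder measure, its threshold, the expected rates and the power are not stated.

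Two other SAP statements bear on the point. A separate analysis of participants with moderate hand weakness is planned, "based on the prior study showing participants with moderate weakness achieved greater gains on the BBT" compared with severe weakness. On error rates, the SAP says "No adjustments were made for multiple comparisons in order to maintain a balance between Type I and Type II error rates", and explains that it does not want to give up power.

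**The concern.** When randomisation balances the arms on a factor that predicts the outcome, the between-stratum part of the outcome variation drops out of the treatment contrast. The ordinary chi-square still counts that part in its variance. Its standard error is then too large, its true level falls below 5%, and real differences are missed more often than necessary.

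Severity is the factor for which this is plausible, since the SAP itself expects different BBT gains by severity. At stake is the power of the second part of each aim's hypothesis, in a plan that gives protecting power as its reason for leaving multiplicity unadjusted.

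**Working it through.** **No figure to reproduce.** The documents give no responder rate, effect size, dropout or power, so neither the 132 nor any responder power can be re-derived.

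**Inputs from the documents:** 132 participants, three arms, four sites, stratification by severity, significance at 0.05.

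**Assumed inputs:** equal allocation (132 / 3 = 44 per arm), a two-sided test without continuity correction, two equal severity levels (22 + 22 per arm), and all responder rates.

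**Step 1, mechanism.** Let p_k be the null responder rate in severity level k and p̄ their mean. The chi-square assumes variance p̄(1 − p̄) × 2/44. With severity balanced, the true variance is W × 2/44, where W is the mean of p_k(1 − p_k). With R = W / [p̄(1 − p̄)], the true level is about 2Φ(−1.96/√R). Example, severe 10% and moderate 50%: p̄ = 0.30, p̄(1 − p̄) = 0.21, W = (0.09 + 0.25)/2 = 0.17, R = 0.810, level 2Φ(−2.18) = 2.9%.

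**Step 2, chi-square against CMH by severity.** The CMH statistic is (A − ΣE_k)² / ΣV_k, with A the responders on CCFES, E_k = m_k n_1k / n_k and V_k = m_k(n_k − m_k) n_1k n_0k / [n_k²(n_k − 1)]. Here m_k is the number of responders in level k, and n_1k, n_0k and n_k are the two arm sizes and their total. Severity odds ratio (OR) = [p_mod/(1 − p_mod)] / [p_sev/(1 − p_sev)]. Simulated results (100,000 or 200,000 trials per row):

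| Control rate, severe / moderate | Severity OR | Level by formula | Chi-square level | CMH level | Treatment OR | Power, chi-square → CMH |
|---|---|---|---|---|---|---|
| 25% / 35% | 1.6 | 4.9% | 5.3% | 5.1% | 3 | 69.5% → 69.4% |
| 20% / 40% | 2.7 | 4.5% | 4.8% | 5.0% | 3 | 66.1% → 68.6% |
| 15% / 45% | 4.6 | 3.8% | 4.1% | 5.0% | 3.5 | 71.1% → 76.2% |
| 10% / 50% | 9 | 2.9% | 3.2% | 5.0% | 3.5 | 60% → 70% |
| 5% / 60% | 28.5 | 1.5% | 1.7% | 5.0% | 4 | 42% → 66% |

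Summing exact binomial probabilities over all 23⁴ = 279,841 possible outcomes agrees with the levels, and with the powers given to one decimal, to within 0.2 percentage points.

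**Step 3, a closer copy of the design.** 132 participants in three-arm permuted blocks within 32 cells (4 sites × 2 severity × 2 age × 2 months post-stroke, levels assumed), 8,000 trials per scenario, only severity prognostic. Level is at a 30% overall rate. The standard error of a power figure near 70% is √(0.7 × 0.3 / 8,000) = 0.5 points.

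| Severity OR | Chi-square level | CMH level | 25% vs 50%, chi-square → CMH | 30% vs 60%, chi-square → CMH |
|---|---|---|---|---|
| 1 | 5.3% | 5.2% | 67.9% → 67.2% | 81.4% → 81.0% |
| 3 | 4.4% | 4.7% | 69.9% → 71.5% | 82.6% → 84.2% |
| 5 | 3.9% | 5.2% | 69.3% → 74.2% | 84.3% → 87.4% |
| 10 | 2.9% | 4.7% | 70.7% → 79.4% | 84.7% → 90.9% |

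At a severity OR of 2, a 100,000-trial run with exact balance gave a chi-square level of 5.1% and powers of 70.1% → 69.8% and 81.4% → 82.3%. With 15% loss and 25% vs 50%, power went from 63.0% to 64.6% (OR 3) and from 62.4% to 66.8% (OR 5).

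**Step 4, cost if severity is not prognostic.** At a severity OR of 1, CMH lost 0.3 to 1.5 points across the runs. Part of that reflects the chi-square itself running at 5.2% to 5.3%.

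**Step 5, other adjustments.** CMH over all 32 cells did worse than the chi-square at severity OR 3 (67.3% against 69.9%), and more so with 15% loss (56.8% against 63.0%). A main-effects logistic score test had more power, but its level was 5.6% to 6.3%, so part of the gain is inflation.

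**The case against.** The strongest reply is that an unadjusted chi-square is a standard, transparent test that does not raise the false-positive rate, and that everything driving the loss is assumed. That stands as far as it goes. The primary endpoint, BBT change at 6 months, is analysed by a mixed model and is untouched by this point.

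The evidence on severity is also thin. The SAP reports a direction for BBT gain and no effect size. It does not say whether moderately weak participants gained more in every arm, which is prognosis, or mainly under CCFES, which is effect modification. Only prognosis makes the test conservative under the null. As the responder measure is not defined, a severity effect on BBT gain need not carry over to responder status.

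A reader might infer that all four stratification factors are strong predictors. The documents do not support this. Age is not discussed as a predictor at all, and site and months since stroke appear only as examples of exploratory moderators. A reader might also infer that the test definitely runs far below 5%. That needs a severity OR of about 9 or more, which nothing in the documents establishes.

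The reply does not remove the asymmetry. Stratifying by severity may gain several points and risks about one.

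**Conclusion.** The point holds as a conditional efficiency loss in a named part of both hypotheses. Its size depends on how strongly severity predicts response:

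- OR 2 or below: about 0 points of power, chi-square level about 5%.
- OR about 3: 1 to 3 points, level about 4.4% to 4.8%.
- OR about 5: 3 to 5 points, level about 4%.
- OR 9 to 10: 6 to 10 points, level about 3%.

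The 24-point gap in the 5% / 60% row (66 − 42) belongs to an OR of 28.5 and should not be read as the expected loss. All figures assume 44 per arm and two equal severity levels. The primary sample keeps only participants who completed treatment, so the real numbers will be smaller and balance on severity is no longer guaranteed. For this hypothesis, the missing responder definition is a larger gap than the choice of test.

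**What to change.** In the SAP, replace the pair-wise chi-square tests with CMH tests stratified by baseline hand-impairment severity, using the same cut as at randomisation. Do this for CCFES against cNMES and for CCFES against TOT. Report the severity-stratified risk difference with its 95% CI, and keep the unadjusted chi-square as a sensitivity analysis.

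Do not stratify on all four factors jointly; the cells are too sparse. Use a covariate-adjusted logistic model only as support. With four sites and two levels for each other factor, treatment plus the stratification factors plus baseline score takes about 8 coefficients. At 30% to 40% response among 88 participants there are about 26 to 35 events, or 3 to 4 per coefficient.

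The cost is a sentence of SAP text, a few lines of code on data already collected, and about 1 power point if severity turns out not to matter. The SAP is written in the past tense; if responder results have already been seen, the CMH analysis should be labelled as added afterwards.
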